The randomization of premiums will provide a discount to some households. Of households that attend the village meeting, 20% of households, up to a maximum of 12 households per village, will win a coupon for 5-months free insurance in the first 6-month cycle, with the option to renew for a second 6-month cycle with a coupon for 3-months free. The remaining households in attendance at the meeting will be entitled to a coupon for a 1-month discount on insurance, which is the usual policy for the SKY program. SKY will be holding village meetings in Takeo, Kandal, and Kampot provinces over the course of the thirteen months from November 2007 to December 2008 (roughly the period during which the baseline survey will be administered). Table 1 shows an approximation of the distribution of the targeted sample across regions. The column "Total Meetings Held" indicates the number of village meetings SKY plans to hold in each district or province and "Total Lucky Draws" indicates the number of Lucky Draws held in the given district. The final column, "% of Villages Surveyed", indicates the approximate percentage of the sample that will come from each area. Note that we will hold Lucky Draws at most village meetings in 2008. We will only survey villages in which we hold a Lucky Draw.

				Total	Total	% of Villages	
				Meetings	Lucky	Surveyed	
				Held	Draws		
Takeo Province			128	128	51%		
Ang Roka village	s (older	villages)		32	32	13%	
Kirivong villages			48	48	19%		
Donkeo villages				48	48	19%	
Kandal Province	74	72	29%				
Koh Thom village	es			74	72	29%	
Kampot Province	50	50	20%				
Kampot villages				50	50	20%	
All Villages				252	250	100%	

Table 1: Targeted Regions

In addition to the randomized intervention, we will also be studying the effect of SKY on the quality and functioning of public health facilities. The fact that higher quality facilities are targeted by SKY means that there can be no valid control group in a longitudinal study, but we will use several methods to measure changes in health center quality over time that will allow us to gain some insight into the impact of SKY.

4. Sampling Strategy

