For the quantitative survey, the main evaluation sample will consist, roughly, of half coupon winners and half non-winners. More precisely, we will interview all large coupon winners, and randomly select an equal number of small coupon winners to interview. In addition, to address the question of selection into insurance, we will oversample households that purchased insurance from the population of small coupon winners. In total, our sample of approximately 5,200 households will consist of approximately 46% large coupon winners and 54% small coupon winners. For the quantitative survey, the main evaluation sample will consist, roughly, of half coupon winners and half non-winners. More precisely, we will interview all large coupon winners, and randomly select an equal number of small coupon winners to interview. In addition, to address the question of selection into insurance, we will oversample households that purchased

insurance from the population of small coupon winners. In total, our sample of approximately 5,200 households will consist of approximately 46% large coupon winners and 54% small coupon winners¹.

The survey team will interview households between two and seven weeks after the village meeting². An Evaluation Representative will attend each village meeting to help run the Lucky Draw lottery. At the end of each village meeting the Evaluation Representative will randomly select a number of the small coupon winners to be interviewed. SKY Insurance Agents will visit these households, as well as all large coupon households, before the 21st of the month. Once all households have had the opportunity to purchase insurance, we will interview these sampled households. Table 2 offers a breakdown of the interview sample.

	Large coupon wi	inners S	Small coupo	n winners	Additional small coupon	Total
	(100% sampled)		(25% sampled) buyers		(50% sampled)	
	1	2	3	4	5	6
	Total	Buyers (est.)	Total	Buyers (est.)	(Estimated)	(Estimated)
Per meeting	9.5	3.8	9.5	0.57	1.8	20.8
Total	2,375	950	2,375	143	453	5,203

Table 2: Quantitative survey sample

Notes: We assume 250 village meetings. Based on the results from the pilot test in 2007, we assume 40% of large coupon winners purchase SKY and 6% of small coupon winners purchase SKY.

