Columns [1] and [3] of Table 2 show the number of large and small coupon winners to be interviewed, respectively. Columns [2] and [4] show the number of buyers that will be interviewed out of those two groups, with sample sizes estimated based on the winter 2007 pilot take-up rates. Column [5] shows the estimated number of additional small coupon buyers we will oversample. Finally, column [6] shows the total number of households interviewed per village and overall.

¹ Actual number and distribution (buyers/non-buyers, etc.) of households will vary depending on village meeting attendance and take-up in each village.

5. Methodology

In this section we detail the four sources of data that will be collected in the evaluation, namely, the household survey, village leader interview, village monographs, health center surveys and health logbooks.

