5.1. Household Survey

The principal component of data collection is a large-scale survey collecting three rounds of quantitative data from approximately 5,200 households. The sampling is described above in section 4 of this protocol.

The baseline will be a rolling survey, administered to each village approximately two to seven weeks after the Lucky Draw is held³. The second round will use the same rolling format, and will be administered 12 months after the baseline. The final survey round will be administered 24 months after the baseline.

This survey will collect data on household demographics, wealth indicators, self-perceived and objective health measures, health care utilization and spending, assets and asset sales, savings, debt, health risk behaviors, willingness to take financial risks, trust of institutions, means of paying for large health expenses, and willingness to trade current for future income. We describe the elements of this survey in detail in Section 6, below.

The survey will ensure high quality data using multiple means. All surveys will be reviewed at the household by the enumerator. All surveys will then be reviewed by a data editor who reviews unclear responses and outliers and checks for data consistency (e.g., mothers who are male or age 7). All surveys will then be reviewed by a field supervisor. The field editor and supervisor also review a subset of questions with a subset of households to check on data quality. These checks will include all very large responses for high health care costs (an important point, as health care costs are dominated by a small number of outliers.) When data are entered, we run a further set of checks for consistency and permissible values. Unexpected answers and outliers lead to rechecking the paper questionnaires.

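### Table 2's 50% sampling label and its 453 additional small-coupon buyers cannot both hold, so the intended fraction must be stated and the figures made to agree

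*Protocol*

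**What the plan says.** Section 3 (Research Design) sets the lottery: "20% of households, up to a maximum of 12 households per village, will win a coupon" of the larger value. Everyone else present is in the small-coupon group: "The remaining households in attendance at the meeting will be entitled to a coupon for a 1-month discount on insurance".

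Section 4 (Sampling Strategy) sets the survey sample: "we will interview all large coupon winners, and randomly select an equal number of small coupon winners to interview". It then adds an oversample of small-coupon households that bought insurance, to serve the study of selection. The summary is: "In total, our sample of approximately 5,200 households will consist of approximately 46% large coupon winners and 54% small coupon winners".

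Table 2 gives, per meeting and overall:

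- large-coupon winners, 100% sampled: 9.5 and 2,375, of whom 3.8 and 950 are expected to buy;
- small-coupon winners, 25% sampled: 9.5 and 2,375, of whom 0.57 and 143 are expected to buy;
- additional small-coupon buyers, 50% sampled: 1.8 and 453;
- total: 20.8 and 5,203.

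The note to the table states its assumptions: "We assume 250 village meetings", and "we assume 40% of large coupon winners purchase SKY and 6% of small coupon winners purchase SKY". The text below the table explains the third group: "Column [5] shows the estimated number of additional small coupon buyers we will oversample". Section 5.1 carries the total forward: "collecting three rounds of quantitative data from approximately 5,200 households".

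**The concern.** The additional buyers can come only from small-coupon households outside the 25% sample. The table's own rates fix the expected size of that pool. Half of it is well under 453, so the printed fraction and the printed count contradict each other.

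The cell matters for three reasons. Small-coupon buyers are the group buying at close to the usual price, so they form one arm of the comparison of buyers at different prices under Objective 2. The fraction also sets a small-coupon buyer's probability of being interviewed, and hence any weight needed to describe small-coupon households or to compare buyers with non-buyers. Finally, the cell feeds the total that sizes three survey rounds.

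**Working it through.** **Inputs, all from the protocol.** 250 meetings; 9.5 large-coupon and 9.5 sampled small-coupon households per meeting; sampling fractions of 25% and 50%; take-up of 40% and 6% (Table 2 and its note); a 20% lottery capped at 12 winners (Section 3).

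**What reproduces.**
- Large-coupon households: 9.5 × 250 = 2,375. Buyers: 2,375 × 0.40 = 950.
- Sampled small-coupon households: 9.5 × 250 = 2,375. Buyers: 2,375 × 0.06 = 142.5, printed as 143.
- Total: 2,375 + 2,375 + 453 = 5,203. Large-coupon share: 2,375/5,203 = 45.6%, printed as 46%.

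Column 5 is therefore the only break, and the total and the split inherit it.

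**Column 5 from the stated rates.**
- Small-coupon households per meeting: 9.5/0.25 = 38. The uncapped lottery gives the same: 9.5 × 80/20 = 38.
- Outside the 25% sample: 38 − 9.5 = 28.5. Buyers among them: 28.5 × 0.06 = 1.71.
- At 50%: 0.855 per meeting, × 250 = 213.75, about 214. Printed: 453, which is 2.1 times as many.

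**The two ways to reconcile.**

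| | Printed | 50% sampled | 100% sampled |
|---|---|---|---|
| Additional buyers per meeting | 1.8 | 0.86 | 1.71 |
| Additional buyers, total | 453 | 214 | 428 |
| Survey total | 5,203 | 4,964 | 5,178 |
| Large/small split | 46/54 | 48/52 | 46/54 |
| All small-coupon buyers interviewed | 596 | 356 | 570 |
| Change from 596 | | −40% | −4% |

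**Other readings of 50%.**
- Half of all small-coupon buyers: 38 × 0.06 × 0.5 × 250 = 285.
- The same, less those already sampled: 285 − 142.5 = 142.5.
- Rates pushed to their rounding limits (9.55 sampled, 24.5%, 6.5%): (9.55/0.245 − 9.55) × 0.065 × 0.5 × 250 = about 239.
- Take-up needed for 453 at 50%: 453/(250 × 0.5 × 28.5) = 12.7%, against 6%.
- Small-coupon households needed for 453 at 50%: 453/(250 × 0.5 × 0.06) + 9.5 = 69.9 per meeting, which makes 9.5 a 13.6% sample, against 25%.

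**What the cap can do.** Above 12/0.20 = 60 attendees the cap binds, and small-coupon households exceed four times the winners, so the mean can exceed 38. For 453 at 100% sampling, the mean must be 453/(250 × 0.06) + 9.5 = 39.7. Then 9.5 is a 23.9% sample of small-coupon households, and 9.5/49.2 = 19.3% of attendees win.

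**Effect on precision.** For comparing 950 large-coupon buyers with the small-coupon buyers (two-sided 5%, 80% power, simple two-sample formula, clustering ignored), the detectable difference in SD units is 2.80 × √(1/950 + 1/n):
- n = 596: 2.80 × 0.0523 = 0.146
- n = 356: 2.80 × 0.0621 = 0.174, with a standard error 19% larger
- n = 570: 2.80 × 0.0530 = 0.148

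**Inclusion probability of a small-coupon buyer.** 0.25 + 0.75 × 0.5 = 0.625 at 50%; 0.25 + 0.75 × 1 = 1.0 at 100%. The inverse weights are 1.6 and 1.0.

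**The case against.** The strongest defence is that the label, not the count, is the slip. The printed 1.8, 453, 20.8, 5,203 and 46/54 all fit near-complete sampling of the remaining buyers, and only the header says 50%. Those figures are not independent, since all pass through column 5, but they suggest which fraction the calculation used. On that reading the total moves by 25.5 households (0.5%) and the split stands. This defence holds as far as it goes: the document does not rule it out.

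A reader might infer that 453 is impossible under any fraction, because it exceeds the 428 buyers left in the pool. That rests on exactly 38 small-coupon households per meeting. The cap of 12 winners can raise that mean, and 39.7 would give 453 exactly. The protocol gives no attendance distribution, so this is possible but not shown.

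Footnote 1 warns that actual numbers will vary with attendance and take-up. That concerns realised against planned numbers and does not reconcile a planning table with its own assumptions. The table's header is broken in the extracted text, so the placement of the 50% label should be checked. The figures themselves are legible and agree with one another, so layout alone does not explain the conflict.

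The protocol states no power target for the price comparison, so the detectable differences above are only a gauge of size.

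**Conclusion.** Table 2 is inconsistent as written: with a 25% sample, 6% take-up and 250 meetings, a 50% fraction gives about 214 additional buyers and cannot give 453. Neither rounding, the cap nor footnote 1 closes that gap.

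A reader might conclude that the 5,203 total and the size of the selection study are overstated. The document does not support that as a settled conclusion. It holds materially only if 50% is the intended fraction: total 4.6% lower, small-coupon buyers 40% fewer, detectable difference 0.174 instead of 0.146 SD. If all remaining buyers are to be interviewed, the printed total and split essentially stand and the fraction is what is wrong.

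Nor does the whole selection objective depend on this cell. Of the five analyses listed under Objective 2, the comparison of buyers at different prices uses this group directly, and weighted buyer versus non-buyer descriptions depend on the fraction. The external data, programme records and village monographs do not rely on it, and the 950 large-coupon buyers also inform the buyer versus non-buyer analysis. The randomised comparison of 2,375 with 2,375 is unaffected.

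**What to change.** State the intended sampling fraction for column 5 and the attendance assumption behind it. Then make column 5, the total, the split in Section 4 and the sample size in Section 5.1 agree.

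- If 50% stands: 0.86 per meeting, 214 additional buyers, a total of 4,964, a 48/52 split and about 356 small-coupon buyers.
- If all remaining buyers are to be interviewed: change the header to 100%, and either restate 1.71, 428 and 5,178 or keep 453 and give the mean attendance that yields it.

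Use the same fraction for any sampling weights: inclusion probability of a small-coupon buyer about 0.625 at 50%, 1.0 at 100%.

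The cost is one table and a few sentences. The 50% version also means acknowledging a smaller usual-price buyer group.

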5.1. Household Survey

The principal component of data collection is a large-scale survey collecting three rounds of quantitative data from approximately 5,200 households. The sampling is described above in section 4 of this protocol.

The baseline will be a rolling survey, administered to each village approximately two to seven weeks after the Lucky Draw is held³. The second round will use the same rolling format, and will be administered 12 months after the baseline. The final survey round will be administered 24 months after the baseline.

This survey will collect data on household demographics, wealth indicators, self-perceived and objective health measures, health care utilization and spending, assets and asset sales, savings, debt, health risk behaviors, willingness to take financial risks, trust of institutions, means of paying for large health expenses, and willingness to trade current for future income. We describe the elements of this survey in detail in Section 6, below.

The survey will ensure high quality data using multiple means. All surveys will be reviewed at the household by the enumerator. All surveys will then be reviewed by a data editor who reviews unclear responses and outliers and checks for data consistency (e.g., mothers who are male or age 7). All surveys will then be reviewed by a field supervisor. The field editor and supervisor also review a subset of questions with a subset of households to check on data quality. These checks will include all very large responses for high health care costs (an important point, as health care costs are dominated by a small number of outliers.) When data are entered, we run a further set of checks for consistency and permissible values. Unexpected answers and outliers lead to rechecking the paper questionnaires.

5.2. Village Leader Interview

In each village, we will interview the village chief or village leader in order to collect general village-level information, including the location of all local health facilities (public, private, pharmacies, traditional healers, etc.), recent villagelevel shocks (drought, flood, epidemics, etc.), availability of lending institutions, seasonal access to roads and price and availability of paid transportation. Because the randomization is at the household level, the information garnered from the village leader will be of greatest use in the selection study (e.g., testing if villages far from regional hospitals have lower take-up), in assessing the external validity of the evaluation, and potentially in estimating the effect of insurance in villages with different characteristics.

³ See previous footnote: the timelag between village meetings and interviews will be longer for households attending earlier village meetings.

5.3. Village Monographs

To better understand how SKY affects outcomes and why people buy and/or drop out of SKY, we will collect detailed village-level information from four villages that have already been exposed to SKY (including two villages in Kandal, where SKY has been present the longest) and two villages in which SKY will enter in 2008. We will interview all past and present SKY members in each village, ten non-SKY members, and representatives of all of the health care providers (public as well as private sector). The resulting village monographs will provide detailed qualitative evidence regarding the dynamics of SKY membership over time (who joins first, who drops out, and why) as well as potential effects of SKY on non-members (e.g., how attitudes towards insurance and health-seeking behavior change). We will also use the interviews to examine how SKY and local health care providers operate and interact in practice. In addition, we will test future rounds of the survey instrument in these villages.

Table 3: Qualitative Villages Targeted

Province	Takeo	Kandal	Total
Current SKY villages	2	2	4
Future SKY villages	2	0	2
Total number of monographs	4	2	6

5.4. Health Center Survey

The main evaluation will be at the household level. At the same time, there are also potentially interesting effects of SKY on health care providers and of health center quality on SKY take-up. Our randomization will not capture these effects directly. Thus, we will use multiple methods to gain some understanding of these effects. To do so we will analyze the following sources of information on health center quality:

• The household survey will measure perceptions of health center quality.

 GRET health center surveys prior to SKY introduction provide quality measures for most facilities.

 The Village Monograph will use in-depth interviews and observation to measure health center quality and to examine how SKY has affected health center quality.

• Subsets of these interview questions will be replicated at roughly ten additional health centers to check whether

results from the in-depth case studies generalize to other health care providers.

 Two waves of a short survey of SKY Member Facilitators will be administered to measure aspects of health center quality that member facilitators can observe. The survey will include Member Facilitator reports on:

Doctor skills and respect for patients

- · Other clinician skills and respect for patients
- · Sufficiency of drugs
- Cleanliness
- · Waiting times (average and longest of the week)
- · Share of scheduled hours the center is open

 Side payments typically paid by SKY and by non-SKY members

• Changes in health center quality since SKY arrived (or since Member Facilitator started working at this health center) We will use all of the data sources to study how the quality of health centers has changed since SKY began in the area⁴.

We will also use each household's perceptions, village-level average perceptions, member facilitator responses, and SKY's baseline measures of health center quality to study

1) whether quality perceptions of households, of Member

The above criteria will be evaluated via random audits of logbook data, comparison with SKY (and perhaps other health center) utilization data, and comparison with recall questions in follow-up household interviews. We will extensively test logbooks during the first months of the roll-out. If logbooks appear valid, we will distribute logbooks on a large scale. We will continue to measure logbook quality via ongoing validity tests, as described above.

⁴ We had initially planned to perform a longitudinal health center survey. Unfortunately, results from such a survey would not be credible. There is not a comparison group to show what changes would have occurred at these health centers without SKY's intervention. For example, if there is a national budget crisis and health center quality declines on average at health centers with SKY contracts – but far more at health centers without a SKY contract – our analysis would erroneously indicate a SKY contract reduced health center quality. Conversely, if average health center quality increases, our results will be biased in favor of showing a benefit for SKY.

Thus, we have reduced the planned data collection at health centers and increased the number of villages where we will collect household data – raising statistical precision for the main analyses. We will still have longitudinal data on health centers, as noted above. Because we are emphasizing qualitative research methods that identify the causal links behind changes we observe, our results should be more credible than a statistical study with more measures but without a comparison group. At the same time, we will explore the Ministry of Health's set of quality indicators and see if a statistical study encompassing both SKY and comparison regions is feasible.

6. Analytical Framework

As discussed in Section 2, this project has the following objectives:

1. to estimate the causal effect of health insurance on households;

2. to understand the determinants of take-up of health insurance; the extent of adverse and positive selection; and the potential for risk-pooling;

3. to identify potential effects of health insurance on public health facilities;

4. to contribute more broadly to the body of knowledge on the effect of health insurance in Cambodia and in developing countries.

6.1. Statistical Methods

To estimate the causal effect of health insurance on household health and economic outcomes, we will implement a number of estimators. The overall econometric technique is to generate multiple estimates of the effect of insurance on the outcomes of interest, thus allowing us to construct a credible range of the estimated program effect. To begin with, we will construct a lower bound for the program effect the Intention-to-Treat effect. Here, outcomes at baseline will be differentiated from outcomes in the follow-up, across large and small coupon winners. This estimate provides a credible lower bound for the true program effect, because many of the large coupon winners will not take up insurance, while some of the small coupon winners will, yielding an underestimate of the true program effect. Formally, we will run a regression that includes a vector of individual fixed effects (individuali) to absorb characteristics of the household or individual, observed or unobserved, that do not change over time and a vector of year fixed effects (year t) to control for changes over time that affect all individuals (or households). We can also control for

This section outlines our methodology for achieving each goal. For objectives 1 through 3, we include a list of indicators that we plan to measure using our survey instruments. Note that the final list of indicators will depend on pre-test results, and on the power we have to measure SKY impacts using each indicator with the given study design.

Methodology for Objective 1: The Causal Effect of Health Insurance

J and I time-variant individual- and household-level covariates (Xjt and Zjit) that might affect health, health care utilization, and other outcomes, e.g., current household income. Thus, we can estimate:

Yjivt = β postit * large-couponi + γ postit + Σ li=1 α Xit + Σ Jj=1 δ Zjit + individualj+ yeart + Uvt + ϵ jivt

In this specification, postit indicates follow-up observations, Uvt represents village-level shocks collected in the village leader survey, and ɛjivt is a random error term representing individual variation from the mean. The coefficient β is the difference-in-differences estimate of the effect of being offered a high-value coupon. Outcome indicators (the Yjivt in the equation above) for Objective 1 are listed below.

A more policy-relevant estimate we will generate is the effect of insurance on those who were induced to take up insurance upon receiving a large coupon (also known as the Local Average Treatment Effect), using the "large coupon" as an instrumental variable for taking up insurance. The details of this estimator are presented in the Statistical Appendix.

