2) health insurance = $\beta_0 + \alpha$ · high-value coupon for insurance + controls + u.

Here, "health insurance" is a variable equal to 1 if a household buys health insurance and 0 if a household does not buy health insurance, and "high-value coupon for nsurance" is a variable equal to 1 if a household wins a high-valued coupon for insurance, and 0 otherwise. The "controls" are any other characteristics that we believe

influence the purchase of health insurance. We can estimate α using a linear probability model (that is, OLS), although other functional forms are possible. We can use the estimated coefficients to predict p[^] ("p-hat"), the probability of having health insurance.

3) number of health center visits = controls + β_{2SLS} · p^A.

Now we can run a second-stage equation:*

As long as the coupon given in the lottery is uncorrelated with baseline health (or other determinants of health center visits), the two-stage least squares estimate β_{2SLS} will be an unbiased estimate of the true effect of health insurance on health center visits. This procedure is called two-stage least

squares or instrumental variables techniques, with the coupon value as the instrument.⁵

It might be simpler to think of the analysis in 2 pieces. We can run a non-causal reduced form equation (where Δ = change in a variable):

4) number of health center visits = controls + γ * high-value coupon for insurance.

Now the coefficient we care about is β , and can be estimated by:

 $\beta^{A} = \Delta$ health center visits / Δ insurance status

= (Δ health center visits/ Δ coupon value) / (Δ (insurance status) / Δ coupon value)

$$= \gamma^{\prime} / \alpha^{\prime}$$
.

That is, the ratio of the coefficient from the reduced form equation (4) (how coupons affect health center visits) to the coefficient from the first stage in equation (2) (how coupons affect insurance uptake) can tell us how insurance affects health center visits. Intuitively, assume coupons are distributed in random lotteries, and having a valuable one leads to a 50 percentage points higher probability of buying insurance. Moreover, assume households with coupon winners also have 1.5 extra health center visits per year (on average). Then it appears the causal link between buying insurance and visiting health centers = 1.5 more health center visits / 50% more insurance = 3 more health center visits for households with (exogenously) higher insurance.

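### One coupon coefficient averages the 12- and 24-month rounds, although the coupon price difference covers only the first two 6-month cycles

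*Protocol*

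**What the plan says.** Section 3 (Research Design) states that large-coupon winners "will win a coupon for 5-months free insurance in the first 6-month cycle". For the period after that cycle it describes a smaller subsidy: these households are left "with the option to renew for a second 6-month cycle with a coupon for 3-months free". All other attendees are "entitled to a coupon for a 1-month discount on insurance". No coupon is described beyond the second cycle.

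Section 5.1 places the baseline about "two to seven weeks after the Lucky Draw is held" and then sets two follow-up rounds. Of the earlier one it says: "The second round will use the same rolling format, and will be administered 12 months after the baseline". Of the later one it says: "The final survey round will be administered 24 months after the baseline".

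The equation in section 6.1 has one coefficient, β, on the product of post and large coupon. Of post it says only: "In this specification, postit indicates follow-up observations". Year effects enter additively, so they shift both arms together and do not let the coupon effect differ between rounds. Equations (5) and (7) of the Statistical Appendix have a single follow-up year.

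In part a of the Statistical Appendix, the insurance regressor "is a variable equal to 1 if a household buys health insurance", with no time index. The surrounding text speaks of having insurance and of insurance status.

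**The concern.** The design works because price moves cover: Table 2 assumes 40% purchase with a large coupon and 6% with a small one. When the price difference ends, the cover difference may narrow. The protocol itself expects lapses: section 3 plans to compare dropout rates, and the Objective 2 methods report much lower renewal among members who had not used a facility.

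Most spending, illness and utilisation indicators are flows over four weeks or 12 months. At the final round their recall windows fall essentially after coupon support. One β then mixes a supported year with an unsupported one, and the reader cannot tell a small effect of the offer from a fading difference in cover. Section 6.1 calls the intention-to-treat estimate a lower bound, but only because of non-take-up and crossover. It does not mention lapse after the subsidy.

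The same timing question reaches the instrumental-variable estimate. If the denominator is purchase at the start and the numerator is an outcome two years later, the ratio is not the effect of being insured.

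**Working it through.** **Inputs from the protocol.** Take-up of 40% and 6%, with 2,375 households per arm in the main sample (Table 2); large coupon 5 then 3 free months and small coupon 1 month (section 3); baseline 2 to 7 weeks after the draw, follow-up 12 and 24 months later (section 5.1); recall of four weeks, or 12 months for major events (section 6.2.1).

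**Reproducing the plan's figures.** 2,375 × 0.40 = 950 and 2,375 × 0.06 = 142.5, printed as 143. Both agree with Table 2. The initial cover gap is 0.40 − 0.06 = 0.34.

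**Timing.**
- Subsidised months in the first 12: (5 + 3) − 1 = 7 more for large coupons. In months 13 to 24 the described difference is 0.
- Round 2 takes place about weeks 52 + 2 = 54 to 52 + 7 = 59 after the meeting. Its four-week recall spans about weeks 50 to 59, at or just past the end of support.
- Round 3 takes place about weeks 104 + 2 = 106 to 104 + 7 = 111. Four-week recall spans weeks 102 to 111. Twelve-month recall starts about week 54 to 59. Both windows lie essentially after support.

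**Dilution of β.** Assume that an effect b acts only while a household is covered and that the rounds have equal weight. Let r12 and r24 be the shares of the initial gap remaining at each round.

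- 12-month coupon effect = 0.34 × b × r12
- Pooled β = 0.34 × b × (r12 + r24)/2
- Ratio of pooled to 12-month = (1 + r24/r12)/2

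No renewal rate is given, so r24 is varied over its whole range with r12 = 1:

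| r24 | gap at 24 months | pooled β | pooled / 12-month |
|---|---|---|---|
| 1.00 | 0.340 | 0.340b | 100% |
| 0.75 | 0.255 | 0.298b | 87.5% |
| 0.50 | 0.170 | 0.255b | 75% |
| 0.25 | 0.085 | 0.213b | 62.5% |
| 0 | 0 | 0.170b | 50% |

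If the gap has already narrowed by 12 months, say r12 = 0.8 and r24 = 0.4, the round-specific effects are 0.272b and 0.136b, and the pooled value is 0.204b. The ratio is again 75%.

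**Instrumental variable.** If the regressor is initial purchase, the pooled ratio is b × (r12 + r24)/2, so 0.75b for r12 = 1 and r24 = 0.5. If it is cover in the same rounds, the ratio is b. Simulation with 4,750 households and 400 runs per scenario agrees: 0.74b for purchase in that case, and 0.99b to 1.00b for current cover in all four scenarios tried.

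**Precision.** Under the fixed-effects model with a balanced panel and equal correlation ρ between rounds, the variance is proportional to 2(1 − ρ) with one follow-up round and 1.5(1 − ρ) with two. The standard-error ratio is √(1.5/2) = 0.87 for any ρ. Pooling has the better signal-to-noise only if (1 + r24/r12)/2 exceeds 0.866, that is, if r24/r12 exceeds about 0.73. With r12 = 1 this is a gap of about 0.73 × 0.34 = 0.25 at 24 months.

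**The case against.** The pooled β is a valid average effect of the offer over the two rounds. Section 6.1 already presents it as a lower bound and promises several estimators. With full retention there is no dilution, and the protocol notes that in 2007 nearly all members who had used a health centre renewed. Above about 73% retention of the gap, pooling is the more efficient choice. Debt, asset loss or stunting may carry the effect of first-year cover forward. All of this stands, and it limits the size of the point. It does not justify a single coefficient, because round-specific terms are right whether effects fade, persist or grow.

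Three stronger readings are tempting but unsupported:

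- A reader might infer that the instrumental-variable estimate at 24 months is divided by the initial 34-point gap. The protocol does not say so. The 40% and 6% are pilot figures used to size Table 2, the first stage is to be estimated, and the appendix alternates between buying and having insurance. The wording is ambiguous; it does not fix a wrong denominator.
- A reader might infer that the coupon's support for renewal breaks the exclusion condition and so makes the insurance effect look too small. Longer cover among households that would have bought anyway, about 6% by Table 2, adds to the outcome difference without entering a purchase indicator. If cover has an effect, that inflates the ratio.
- A reader might take the 12-month round as a clean 34-point year. For four-week outcomes it falls at the edge of support, so its gap may be smaller too.

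**Conclusion.** The point holds for the stated equation. β averages a round that follows the supported year with one that follows a year without any described coupon price difference. For flow outcomes the pooled value is 50% to 100% of the 12-month coupon effect. This range assumes equal round weights, an effect that acts only during cover, and the 12-month gap intact. The position within the range depends on renewal, which the documents do not give. The documents do not support a claim that all outcomes are diluted, or that the instrumental-variable estimate is wrong by a known amount. For the latter, the finding is that the timing of the insurance variable is undefined and must be fixed. A loss of power cannot be computed, because the protocol states no effect size, standard deviation or power.

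**What to change.** In section 6.1, replace the single post-by-large-coupon term with two interactions, one for each follow-up round. Report the 12-month coefficient as the effect over the period of coupon support, noting that four-week outcomes fall at its end. Report the 24-month coefficient as persistence afterwards. The pooled average can stay as a secondary estimate.

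In part a of the Statistical Appendix, give the insurance variable a time index and run the first stage separately by round, with SKY cover measured for that round. For stock outcomes such as debt or stunting, use cumulative months of cover since the lottery, because cover in the recall window alone would leave earlier cover as a separate path from coupon to outcome. Earlier cover can raise the same problem for four-week outcomes, so state the assumption there. Numerator and denominator then refer to the same period.

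Costs: each round-specific estimate has a larger standard error than the pooled one (pooled is about 0.87 of single-round), and the 24-month instrumental-variable estimate will be imprecise if little of the gap remains. Cover by round needs either household-level linkage to SKY membership records or a survey question. The Objective 2 methods plan to use those records but do not state a link to the survey households.
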